4. STUDY ENROLLMENT AND WITHDRAWAL

4.1. Inclusion Criteria

To be included in the study, subjects must meet the following inclusion criteria.

1. Subject is of either gender between 12 and 70 years of age, inclusive.
2. Subject (or parent/legal guardian) has the ability and willingness to sign a written informed consent.
3. Subject has a diagnosis of chronic (≥ 1 year), stable atopic dermatitis (AD) according to Hanifin and Rajka [Hannifin 1980]
4. Subject has $\geq 5\%$ and $\leq 30\%$ body surface area (BSA) of AD involvement excluding the scalp and groin.
5. Subject has an Investigator's Global Assessment (IGA) score of moderate (3) atopic dermatitis on the 5-point IGA (0-4) scale.
6. For selected photography sites, subject has a target lesion 25 to 200 cm² in surface area on the trunk, upper extremities or lower extremities with a Baseline Signs of AD score of ≥ 6 and ≤ 12 .
7. Subject is in good general health without clinically significant hematological, cardiac, respiratory, renal, endocrine, gastrointestinal, psychiatric, hepatic, or malignant disease, as determined by the investigator.
8. Subject has suitable venous access for blood sampling.
9. Subject is able and willing to complete the study and to comply with all study instructions and attend the necessary visits.
10. Male subjects and their partners must agree and commit to use a barrier method of contraception throughout the study and for 90 days after last study drug application.
11. A negative urine pregnancy test (UPT) result for all WOCBP at the Screening Visit and Baseline Visit. A WOCBP is one who is not permanently sterilized or not postmenopausal. Postmenopausal is defined as 12 months with no menses without an alternative medical cause.
12. Sexually active women must agree to use the following throughout the study and for 30 days after last study drug application. WOCBP who are not sexually active at Baseline and become sexually active must identify a plan for contraception.
 - a. One of these highly effective contraception methods
 - i. Intrauterine device (IUD); hormonal (injections, implants, transdermal patch, vaginal ring; tubal ligation; partner vasectomy, OR
 - b. Oral contraceptives WITH a barrier method (listed below), OR
 - c. Two barrier forms of contraception (listed below)
 - i. Male or female condom; diaphragm; cervical cap; contraceptive sponge.
13. Males subjects must refrain from sperm donation during the study treatment period and until 90 days after last study drug application.

4.2. Exclusion Criteria

If a subject meets any of the following exclusion criteria, they may not participate in the study.

1. Female subject who is breast feeding, pregnant, or planning to become pregnant.
2. Subject who has an IGA score of 2 (mild) or 4 (severe).
3. Subject with history of known or suspected intolerance to the drug product excipients (hexamethyldisiloxane, polypropylene glycol (PPG) 15 stearyl ether, silicone gum, and isopropyl alcohol).
4. Subject has any clinically significant active infection in the investigator's opinion. This includes active impetigo at any AD lesion.
5. Subject has known Hepatitis-B, Hepatitis-C, or HIV infection.
6. Subject has excessive body or facial hair that would interfere with the evaluation of safety or with the diagnosis or assessment of AD.
7. Subject has sunburns, unevenness in skin tones, tattoos, scars, excessive hair, freckles, birthmarks, moles, or other skin damage or abnormality that would result in the inability to evaluate the AD lesions.
8. Subject has clinically significant or severe allergies that in the investigator's opinion would interfere with participation in the study.
9. Subject has known intolerability to topical treatments e.g., reports excessive burning/stinging or pain with use of topical treatments.
10. Subject has an active or potentially recurring skin conditions(s) other than AD that in the investigator's opinion would interfere with participation in the study.
11. Subject has unstable AD consistent with a requirement for high-potency corticosteroids.
12. Subject has used dupilumab (Dupixent) within 12 weeks prior to the Baseline Visit.
13. Subject has used any biologic therapy, other than dupilumab, within 28 days prior to the Baseline Visit.
14. Subject has used systemic (oral, IV or IM) corticosteroids within 28 days prior to the Baseline Visit. Intra-articular injection for arthroses allowed.
15. Subject has used topical anti-pruritics (e.g., PDE4 inhibitors) within 28 days prior to the Baseline Visit.
16. If subject is taking oral antihistamines, subject has not been on a stable dose of oral antihistamines within 28 days prior to the Baseline visit.
17. Subject has used phototherapy, tanning beds, or any other artificial light device within 28 days prior to the Baseline Visit.
18. Subject has used topical corticosteroids within 14 days prior to the Baseline Visit.
19. Subject has used topical calcineurin inhibitors within 14 days prior to the Baseline Visit.
20. Subjects has used barrier creams (e.g., Mimyx, Atopiclair), within 7 days prior to the Baseline Visit.

21. Subject has an underlying disease that requires the use of interfering topical or systemic therapy.
22. Subject has other dermatological conditions that require the use of interfering topical or systemic therapy or that might interfere with study assessments such as, but not limited to, acne or rosacea.

Note: Treatment with any of the medications noted in Exclusion 11 through 22 is prohibited throughout the study. Use of bland emollients once daily to manage dry skin areas around, but not overlapping, the treatable AD involved areas is acceptable.

23. Subject has a clinically relevant history or currently suffering from any disease or condition that, in the opinion of the investigator, may affect the evaluation of the study product or place the subject at undue risk or interfere with the subject's participation in the study. This may include respiratory (including chronic unstable asthma requiring repetitive drug interventions or hospitalization), gastrointestinal, renal, hepatic, haematological, lymphatic, neurological, cardiovascular, psychiatric, musculoskeletal, genitourinary, immunological, or connective tissue diseases or disorders. Subjects with other dermatologic conditions, including genetic syndromes that have an eczematous dermatitis as a component of the disease (e.g., Netherton's) are excluded.
24. Subject has a clinically relevant history of or current evidence of abuse of alcohol or other drugs. Subjects may be deemed eligible if the UDS identifies subject-reported, prescribed drugs or appropriate levels of alcohol, as determined by the investigator.
25. Subject is currently using any medication that, in the opinion of the investigator, may affect the evaluation of the study product or place the subject at undue risk.
26. Subject has participated in another investigational drug or device research study within 30 days of the Screening Visit or five half-lives of the drug, whichever is longer.
27. Any other reason that would make the subject, in the opinion of the Investigator or sponsor, unsuitable for the study.

4.3. Reasons for Withdrawal or Termination

If a subject is withdrawn from the study, the subject's enrollment in the study will terminate and study drug application will be discontinued. Efforts will be made to perform all assessments scheduled for the Day 85 Visit prior to subject withdrawal. Subjects may be replaced after consultation with the sponsor.

A subject may be withdrawn from further study participation under the following circumstances:

- At the subject's request.
- Noncompliance with protocol by the subject as determined by the study site staff and investigator.
- Adverse Event (decision to be removed from study made by either the investigator or subject). The investigator must notify the sponsor immediately if a subject is withdrawn because of an AE.

- Decision by the investigator or sponsor that termination is in the subject's best medical interest or administrative decision for a reason other than that of an AE.
- Lost to follow-up, as determined by failure to respond to at least 2 telephone calls followed by certified letter sent to the subject's last known address. All attempts to contact the subject must be documented in the subject's source documents.
- Sponsor decision to halt the entire study.

4.4. Premature Termination or Suspension of Study

This study may be suspended or prematurely terminated if there is sufficient reasonable cause. Written notification, documenting the reason for study suspension or termination, will be provided by the suspending or terminating party to the investigator. If the study is prematurely terminated or suspended by the sponsor, the PI will promptly inform the Human Research Ethics Committee (HREC) or Institutional Review Board (IRB) and will provide the reason(s) for the termination or suspension.

Circumstances that may warrant termination or suspension include, but are not limited to:

- Determination of unexpected, significant, or unacceptable risk to subjects
- Insufficient compliance with protocol requirements
- Data that are not sufficiently complete and/or evaluable

The study may resume once concerns about safety, protocol compliance, or data quality are addressed and satisfy the sponsor and HREC/IRB.

5. STUDY DRUG

5.1. Study Drug

5.1.1. Acquisition

Study drug will be provided to the US study sites by The Coghlan Group (TCG) in Bastrop, Texas, USA and to the Australian sites by PCI Pharma Services (PCI) in Port Melbourne, Victoria, Australia. Initial shipments will be made to supply the study sites prior to enrollment of the first subject. Additional supplies will be made available as needed based on subject enrollment.

5.1.2. Formulations, Appearance, Packaging, and Labeling

Botanix Pharmaceuticals' BTX 1204 contains the active pharmaceutical ingredient, cannabidiol (CBD). CBD is a member of a broader family of compounds known as cannabinoids, a class of compounds originally derived from the *cannabis sativa* plant. [Olah 2014] CBD is chemically synthesized under Good Manufacturing Practices (GMP) for use in this study.

BTX 1204 4% Liquid Formulation (active) is a clear to slightly yellow liquid solution with a 4% (w/w) concentration of CBD in a formulation of excipients, which have been used extensively in other topical products. These excipients include hexamethyldisiloxane, silicone gum, polypropylene glycol (PPG) 15 stearyl ether, and isopropyl alcohol (IPA). The solution spreads easily and quickly evaporates leaving the CBD on the skin.

Each milliliter of the BTX 1204 4% (w/w) Liquid Formulation contains 30.0 mg of CBD. The Vehicle will be identical to the BTX 1204 4% (w/w), but without the CBD.

Study drug, active and vehicle, will be supplied in 125 mL multi-dose, metered pumps delivering 0.5 mL per actuation. Each pump will contain approximately 100 mL of study drug. Each subject will apply up to 7 mL per dose. This will require 14 actuations of the pump. Each dose will cover all the subject's AD lesions (except scalp and groin).

Pumps for all groups will be labeled identically, except for kit number and bottle number, to maintain the blind.

Study drug will be applied directly to the AD lesion and spread to cover the AD lesion and up to 1 cm of the surrounding non-lesional skin. For lesions that cannot be accessed for direct application, study drug will be pumped into the palm of one hand and applied to the AD lesions.

Adequate study drug will be provided in kits for daily applications (BID) through 4 weeks (Day 28). Prior to distribution, pumps will be weighed by clinical site staff and the weights recorded in the source documents and the eCRF. When a subject is enrolled, the site will access the IWRS to receive a kit number for the first 28 days of dosing based on the IWRS randomization.

At the Day 29 and Day 57 Visits, the site will access the IWRS to obtain the kit number for the following 28 days of dosing. All distributed pumps will be returned by the subject at the Day 29, Day 57, and Day 85 Visits and weighed to monitor compliance and document doses delivered.

The study drug bottle may include the following information:

Caution: New Drug--Limited by Federal (or United States) law to investigational use only.

KEEP OUT OF REACH OF CHILDREN

Drug Ingredient: BTX 1204 or Vehicle

Directions: Use in accordance with study drug application instructions.

FOR TOPICAL APPLICATION ONLY.

Protocol # BTX.2018.003

Flammable. Store between 15-30°C.

Bottle # _____

Kit # _____

Sponsor: Botanix Pharmaceuticals Ltd

5.1.3. Product Storage and Stability

The study drug will be stored at a controlled room temperature of 15°C to 30°C and should not be refrigerated. Prior to dispensing to the subject, the study drug will be stored in a secured location with access only by authorized study personnel. Study drug has been tested to ensure that there is adequate stability for the duration of the study. Retest dates may be included on the carton labeling.

5.1.4. Preparation

No preparation of the study drug is required.

5.1.5. Dosing and Administration

Subjects will receive their initial application of study drug on Day 1 at the clinical sites administered by the clinical site staff. When the subject is ready for study drug application, a pump is selected from the assigned study kit. The clinical site staff will unlock the pump and apply the first dose of the study drug to the subject's AD lesions. Study drug will be applied to the lesions and up to 1 cm of surrounding non-lesional skin. Study drug will not be applied to AD lesions located on the scalp and the groin.

Subjects will be instructed in how to apply study drug. After their first application in the clinic subjects will apply their study drug at home. Each application of study drug will occur at the approximately the same time in the morning with the second application approximately 8 to 12 hours later. Subjects will apply study drug at the clinical site during the Day 15, Day 29, and Day 57 Visits. A diary will be maintained documenting compliance with the self-administered applications. All study drug pumps (used and unused) will be returned to the clinical site and weighed on the Day 29, Day 57, and Day 85 Visits.

Study drug should not be applied to the eyes or mouth. If study drug accidentally gets into the eyes, the subject should flush their eyes with clear, running water. Subjects are to thoroughly wash

their hands after study drug application. The study drug must not be handled by a family member or caregiver for study drug application.

5.1.6. Starting Dose

The dose for all subjects will be up to 7 mL applied BID to cover their AD lesions and surrounding skin, except on the scalp and the groin. No escalation of dose will occur.

5.1.7. Dose Adjustments/Modifications/Delays

There are no pre-planned dose adjustments, modifications, or delays.

5.1.8. Duration of Therapy

Subjects will receive BID application of study drug for 84 days with a final application on the evening of Day 84 for a total of 168 doses. If the Day 85 Visit is delayed, the subject should continue dosing through the evening before the scheduled Day 85 Visit.

5.1.9. Tracking of Dose

All subjects will be required to maintain a diary documenting each application of study drug. The subject will record that they applied each study dose. Subjects will return the study drug pumps (used and unused) at visits 29, 57, and 85. The clinical site staff will review the diary and count and weigh used/unused pumps to ensure subject compliance with dosing.

5.2. Study Drug Accountability Procedures

At each study visit the clinical site will weigh each pump dispensed to the subject and returned from the subject to calculate the amount (grams) of study drug used. The investigator will keep a current and accurate inventory of all clinical supplies received. These records will be reviewed at each monitoring visit performed by the CRA per SOPs. In case of drug accountabilities discrepancies (missing pump, lost pump or non-compliance cases in which more product was used compared to expected use), investigators should obtain more information and explanation from the subjects.

6. STUDY PROCEDURES AND SCHEDULE

6.1. Study Specific Procedures/Evaluations

At the Screening Visit (Visit 1), all subjects will review and sign an informed consent/assent form attesting to their knowledge of the study requirements, risks, and benefits. The following study specific procedures will occur for all subjects at the Screening Visit:

- Demographics, height and weight, and a medical history will be obtained by the principal investigator or designee.
- A review of systems will be conducted by the principal investigator or designee.
- All WOCBP will have a UPT conducted. The test must be negative for the subject to be enrolled.
- A urine drug screen (UDS) will be conducted to ensure that the subject is not taking drugs of abuse.
- The total body surface area (BSA) of atopic dermatitis involvement will be obtained. The BSA can be approximated using the Rule of 9s or the palm (1%) method.
- An IGA will be conducted. The subject must have an IGA score of moderate (3) (see Table 2).
- The subjects will be queried for concomitant medications that they are currently taking. Concomitant medications include all prescribed and over the counter (OTC) medications and any supplements.
- Eligibility criteria will be reviewed to determine if subjects may proceed to study enrollment.
- At selected sites, a target lesion will be identified. Photographs will be obtained of the target lesion and the target lesion will be scored used the Signs of AD scoring.

If subjects are eligible upon screening, they may be enrolled into the study on the same day.

At various visits throughout the study, the following will occur for all subjects to monitor the safety of the study drug treatment:

- Blood draws will be conducted for CBC and chemistry analysis
- Collection of urine will occur for a urinalysis
- Signs of AD score will be assessed (See Table 3).
- Subjects will be queried to report any AEs that have occurred since the last visit.
- Subjects will be queried to report any new medications or changes in current medications.

Efficacy will be assessed through collection of the IGA, Signs of AD score, BSA of AD, EASI score, and changes in pruritus. An IGA will be conducted at Screening to ensure subject eligibility and again at Baseline (if not same day as Screening Visit) and Days 15, 29, 57 and 85. The IGA assesses the overall status of the AD lesions at the time of the assessment. Every effort should be made to have the IGA conducted by the same investigator/sub-investigator at each visit. No comparisons are made to previous assessments. The IGA is scored from 0 (Clear) to 4 (Severe) based on scoring system provided in Table 2.

Table 2 Validated Investigator Global Assessment scale for Atopic Dermatitis (vIGA-ADTM)^a

Instructions:

The IGA score is selected using the descriptors below that best describe the overall appearance of the lesions at a given time point. It is not necessary that all characteristics under Morphological Description be present.

Score	Morphological Description
0 – Clear	No inflammatory signs of atopic dermatitis (no erythema, no induration/papulation, no lichenification, no oozing/crusting. Post-inflammatory hyperpigmentation and/or hypopigmentation may be present.
1 - Almost clear	Barely perceptible erythema, barely perceptible induration/papulation, and/or minimal lichenification. No oozing or crusting.
2 – Mild	Slight but definite erythema (pink), slight but definite induration/papulation, and/or slight but definite lichenification. No oozing or crusting.
3 – Moderate	Clearly perceptible erythema (dull red), clearly perceptible induration/papulation, and/or clearly perceptible lichenification. Oozing and crusting may be present.
4 – Severe	Marked erythema (deep or bright red), marked induration/papulation, and/or marked lichenification. Disease is widespread in extent. Oozing or crusting may be present.

Notes:

1. *In indeterminate cases, please use extent to differentiation between scores*

For example:

- *Patient with marked erythema (deep or bright red), marked papulation and/or marked lichenification that is limited in extent, will be considered “3 – Moderate”.*

2. *Excoriations should not be considered when assessing disease severity.*

^a Copyright ©2017 Eli Lilly and Company – Used with the permission of Eli Lilly and Company under a Creative Commons Attribution-NoDerivatives 4.0 International License – <https://creativecommons.org/licenses/by-nd/4.0/>

The Signs of AD score will be an examination of all lesions on the subject for the presence of erythema, exudation, excoriation, induration/papulation, and lichenification. Each sign will be graded according to the grade and definitions provided in Table 3.

Table 3 Signs of Atopic Dermatitis (Paller)

Score	Grade	Definition
Erythema (redness)		
0	None	No redness
1	Mild	Mildly detectable erythema; pink
2	Moderate	Dull red; clearly distinguishable
3	Severe	Deep, dark red; marked and extensive
Exudation (oozing and crusting)		
0	None	No oozing or crusting
1	Mild	Minor or faint signs of oozing
2	Moderate	Definite oozing or crusting
3	Severe	Marked and extensive oozing or crusting
Excoriation (evidence of scratching)		
0	None	No evidence of excoriation
1	Mild	Mild excoriation
2	Moderate	Definite excoriation
3	Severe	Marked, deep, or extensive excoriation
Induration/papulation		
0	None	None
1	Mild	Slightly perceptible elevation
2	Moderate	Clearly perceptible elevation but not extensive
3	Severe	Marked and extensive elevation
Lichenification (epidermal thickening)		
0	None	No epidermal thickening
1	Mild	Minor epidermal thickening
2	Moderate	Moderate epidermal thickening; accentuated skin lines
3	Severe	Severe epidermal thickening; deeply accentuated skin lines

The EASI score will be conducted by the principal investigator or an appropriately trained designee to obtain a score to measure the extent (area) and severity of AD. EASI will be scored using the area score for each of the four regions (head and neck, trunk, upper limbs, and lower limbs) of the body. The area score is the percentage of skin affected by atopic dermatitis (eczema) for each body region:

Area score: Percentage of skin affected by eczema in each region

0	No active eczema in this region
1	1–9%
2	10–29%
3	30–49%
4	50–69%
5	70–89%
6	90–100%: the entire region is affected by eczema

At each study visit, the subject will complete the Itch Numeric Rating Score (I-NRS).

I-NRS

The subject will be asked, “How would you rate your AVERAGE itch in the past 24 hours, on a scale from 0 to 10, where 0 is No itch and 10 is Worst itch imaginable?”

Prior to morning application of the study drug, the subject will record in their diary the Worst Itch Numeric Rating Score (WI-NRS).

Each day the subject will complete the Worst-Itch Numeric Rating Score (WI-NRS).

WI-NRS

The diary question will read, “How would you rate your WORST itch in the past 24 hours, on a scale from 0 to 10, where 0 is No itch and 10 is Worst itch imaginable?”

For all subjects, assessment of compliance with study drug application will be conducted through collection of a study diary on which subjects will record their daily administration. In addition, subjects will be required to return all used and unused study drug at each visit where the study site will assess compliance. At each study visit the clinical site will weigh each pump dispensed to the subject and returned from the subject to calculate the amount of study drug used.

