Baseline Visit. Review of eligibility criteria will be repeated. Signs of AD and the EASI scores will be obtained. Subjects will be asked to rate their pruritus using the itch numeric rating score (I-NRS) which is an average level of itch over the past 24 hours on a scale of 0 (no itch) to 10 (worst imaginable itch). At selected sites, photographs and Signs of AD scoring of the target lesion will be obtained. Subjects will be randomized 1:1 using an Interactive Web-based Response System (IWRS) to receive active BTX 1204 4% or Vehicle. Subjects will receive their first dose of study drug applied by the site staff and will be observed in the clinic for approximately 15 minutes after the initial application. Subjects will be given 4 weeks of study drug and instructed in the proper application for twice daily (BID) applications to cover their AD lesions, except on the scalp and groin.

Subjects will be provided with a diary to record their daily pruritus score using the worst itch numeric rating score (WI-NRS). Subjects will record the WI-NRS over the past 24 hours each day prior to their morning application. Subject will also record on the diary the time of their morning and evening applications of study drug.

Subjects will return to the clinic on Day 15. Subjects will be queried for adverse events and changes in concomitant medications since their previous visit. Returned study drug will be weighed and diaries will be reviewed for compliance. The site will obtain IGA, BSA of AD, Signs of AD score, EASI score. Subjects will be asked to rate their pruritus using the I-NRS. The subject will then apply their dose of study drug during the visit for the clinical site to confirm correct application techniques.

Subjects will return to the clinic on Day 29 and Day 57. Subjects will be queried for adverse events and changes in concomitant medications since their previous visit. A UPT will be done on WOCBP. Returned study drug will be weighed and diaries will be reviewed for compliance. The site will obtain IGA, BSA of AD, Signs of AD, and EASI Score. Subjects will be asked to rate their pruritus using the I-NRS. At selected sites, the target lesion will be photographed and scored with the Signs of AD score. The subject will then apply their dose of study drug during the visit for the clinical site to confirm correct application techniques. Another four weeks of study drug will be dispensed along with a new diary.

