3.2. Study Endpoints

The primary endpoint for the study is the proportion of subjects with an Investigator's Global Assessment (IGA) success defined as an IGA score of "Clear" (0) or "Almost Clear" (1) with at least a 2-grade improvement from Baseline at Day 85.

The secondary endpoints for the study are:

- The proportion of subjects with an EASI 75 score at Day 85,
- The proportion of subjects with an EASI 50 score at Day 85,
- The change from Baseline in the Signs of AD score at Day 85,
- The proportion of subjects with an IGA of Clear or Almost Clear at Day 85,
- The proportion of subjects with at least a 2-grade improvement in ISGA from Baseline at Day 85,
- The change from Baseline in the percent of body surface area (BSA) affected by AD at Day 85,
- The time to achieve IGA success, and
- The change from Baseline to Day 85 in the Itch-Numerical Rating Scale (I-NRS)

Exploratory analyses will be conducted for:

- The change from Baseline in the Signs of Atopic Dermatitis score at Day 15, Day 29, and Day 57,
- The change from Baseline in the percent of body surface area (BSA) affected by AD at Day 15, Day 29, and Day 57,
- The proportion of subjects with IGA success defined as an IGA score of "Clear" (0) or "Almost Clear" (1) with at least a 2-grade improvement from Baseline at Day 15, Day 29, and Day 57,
- The absolute and percent change from Baseline in the Eczema Area Severity Index (EASI) score at Day 15, Day 29, Day 57, and Day 85,

- Change from Baseline in the subject's reports of pruritus obtained daily on a Patient Diary,
- Time to improvement of pruritus (change of ≥ 4 in the Worst Itch Numerical Rating Score [WI-NRS, 0 – 10 score]),
- Subject's assessment of the change in their AD from Baseline to Day 85 (Patient Reported Outcome [PRO]), and
- The change from Baseline to Day 29, and Day 57, and Day 85 in the Signs of AD score for the target lesion (selected sites).

Safety outcome measures to be assessed are:

- Reported adverse events (AEs) including treatment-emergent (TEAE) monitored from time of consent through the end of study,
- Changes in clinical labs including complete blood count (CBC), chemistry, and urinalysis between Baseline and Day 85, and
- Subject's reports of burning/stinging obtained during visits on Day 1, Day 15, Day 29, Day 57, and Day 85.

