6.3.2. Baseline Visit

If the subject is deemed eligible and proceeds to enrollment on the same day, in addition to the screening assessments the following will be conducted:

- Collect blood sample for CBC and chemistry
- Collect urine sample for urinalysis
- Assess Signs of AD prior to application of study drug
- Collect EASI score prior to application of study drug
- Collect I-NRS prior to application of study drug
- Randomize subject to study drug treatment
- Apply study drug on subject's AD lesions (see Section 5.1.5)
- Monitor subject for AEs 15 minutes after application of study drug
- Photographs and Signs of AD scoring of target lesion (selected sites only)
- Train subject in proper application of study drug
- Weigh and dispense study drug
- Dispense study diary (Day 1 through Day 28) and train the subject in entering administration times and daily pruritus score.

If the subject is not enrolled on the same day as the Screening Visit, the following will be conducted at the Baseline Visit:

- Review eligibility criteria
- Review medical history and review of systems
- Query subject for adverse events since the signing of the informed consent/assent and changes in concomitant medications
- Collect blood sample for CBC and chemistry
- Collect urine sample for urinalysis
- Conduct UPT (WOCBP only)
- Collect urine sample for UDS
- Perform IGA prior to application of study drug
- Calculate BSA of total AD involvement
- Assess Signs of AD score prior to application of study drug
- Collect EASI score prior to application of study drug
- Collect I-NRS prior to application of study drug
- Photographs and Signs of AD scoring of target lesion (selected sites only)
- Randomize subject to study drug treatment
- Apply study drug on subject's AD lesions (see Section 5.1.5)
- Monitor subject for AEs 15 minutes after application of study drug
- Train subject in proper application of study drug
- Weigh and dispense study drug

- Dispense study diary (Day 1 through Day 28) and train the subject in entering administration times and daily pruritus score.

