#### **6.1.2 Baseline Definition**

Baseline is defined as the last non-missing assessment prior to first application of study drug.

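### The protocol does not require a worst-itch (WI-NRS) score before the first application, so two exploratory itch endpoints may lack an untreated baseline

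*Protocol*

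**What the plan says.** Protocol Section 3.2 lists two exploratory endpoints built on the daily diary score. One is the change from Baseline in the subject's "reports of pruritus obtained daily on a Patient Diary". The other is "Time to improvement of pruritus (change of ≥ 4 in the Worst Itch Numerical Rating Score", on the 0 to 10 scale.

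The diary is the only described source of WI-NRS. The Protocol Summary (Methods) states: "Subjects will be provided with a diary to record their daily pruritus score using the worst itch numeric rating score (WI-NRS". It gives the timing as: "Subjects will record the WI-NRS over the past 24 hours each day prior to their morning application". Section 6.1 repeats the rule: "Prior to morning application of the study drug, the subject will record in their diary the Worst Itch Numeric Rating Score (WI-NRS".

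The Baseline Visit lists in Section 6.3.2 both end with: "Dispense study diary (Day 1 through Day 28) and train the subject in entering administration times and daily pruritus score". Section 5.1.5 has site staff give the first application on Day 1.

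The only explicit analysis definition of Baseline is in SAP Section 6.1.2: "Baseline is defined as the last non-missing assessment prior to first application of study drug".

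**The concern.** Both endpoints compare later worst itch with worst itch before treatment. If the first WI-NRS is recorded after the first application, it does not qualify as Baseline under the SAP definition. LOCF (SAP Section 6.1.5) cannot help, because there is no earlier value to carry forward.

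The alternative is to use the first diary entry as baseline. That measures change from a state treatment may already have altered, and possibly altered differently in the two arms. The I-NRS taken before dosing is no substitute: it asks about average itch and WI-NRS about worst itch, so the difference between them is not a change score.

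Unlike an analysis choice, this cannot be corrected after the visit.

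**Working it through.** The plan states no figure to reproduce. The check traces the order of events on Day 1 and compares it with the Baseline definition.

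1. **Before the Baseline Visit.** The Screening list (Section 6.3.1) issues no diary, and Table 4 first dispenses one at the Baseline Visit. No WI-NRS can exist before that visit.

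2. **At the Baseline Visit.** Section 6.3.2 ties Signs of AD, EASI and I-NRS explicitly to the time before the first dose. WI-NRS is absent from both lists, and the pruritus row of Table 4 is I-NRS alone. Diary dispensing and training carry no such timing instruction. They come last in both lists, after the application and the 15-minute observation, and the Protocol Summary narrative gives the same order.

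3. **First entry that clearly meets the recording rule.** The subject needs the diary in hand and a morning application still to come. If the diary is handed over after the clinic dose, that is the morning of Day 2. By then two applications are due: the clinic dose and the Day 1 evening dose at home (Table 4).

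4. **What a first entry after dosing would cover.** The recall period is 24 hours. If the entry is made h hours after the first application, the pre-dose part of the recall is max(0, 24 − h) hours.
   - Day 2 entry at the same clock time as a Day 1 morning dose: h = 24, so 24 − 24 = 0 pre-dose hours.
   - Clinic dose given later in the day than the Day 2 entry: h is below 24 and some pre-dose hours remain.
   - Day 1 entry at the evening application, 8 to 12 hours after the first (Section 5.1.5): 24 − 8 = 16 down to 24 − 12 = 12 pre-dose hours. The recording rule does not call for this entry.

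   Because the question asks for the worst itch, any remaining pre-dose hours can still set the score. In each case the entry itself postdates the first application, so it does not meet SAP Section 6.1.2.

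5. **What the SAP does with WI-NRS.** Neither endpoint appears in SAP Sections 5.1.2 or 5.1.3. Section 6.8 covers I-NRS but not WI-NRS, and the itch listing (16.2.6.4) is average itch only. Section 8, which records changes to the planned analyses, does not mention dropping them. Protocol Section 9.3.3 still says time to improvement of pruritus will be presented.

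**The case against.** The strongest reply is that a pre-dose entry is already implied. The first diary starts at Day 1 and includes the daily pruritus score, entries are due before the morning application, and Section 6.3.3 places the first application in the morning. Read together, these suggest a Day 1 entry before the clinic dose. This reading is possible and has to be allowed. It is not the only one, since a diary that must record the Day 1 evening home application would also start at Day 1.

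List order is also weak evidence. Weighing and dispensing study drug is listed after applying it, although the first dose comes from the assigned kit, and the photography item sits in different places in the two lists. That stands. The point therefore rests mainly on the missing instruction, not on the sequence.

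Three stronger readings are tempting:

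- *The endpoints cannot be computed.* The documents do not support this, because a site that reads the diary dates as above would have a valid pre-dose value.
- *A late baseline shrinks the measured change by a definite amount.* No first-day effect on worst itch is given anywhere. Section 1.2.3 names application-site pruritus among the most common adverse events in the earlier study, so early itch could rise as well as fall. Both arms could be affected, and no bias in the treatment comparison is shown.
- *A planned SAP result is already biased.* The SAP plans no WI-NRS analysis. The daily means and graphs in Protocol Section 9.3.3 need no baseline.

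**Conclusion.** The point holds as a gap in the written requirement. WI-NRS comes only from a diary first issued at the visit where dosing starts, and nothing requires an entry before the first application. Subjects who follow the written sequence may have no valid WI-NRS baseline, or one affected by treatment in an uncertain direction.

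The share affected lies between none and all. It depends on the diary form and site training, which the documents do not show. The conclusion assumes that no other study material requires a pre-dose entry.

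The consequence is small. Both endpoints are exploratory, and the primary endpoint does not use itch. The secondary itch endpoint uses I-NRS, which is collected before dosing. This is a low-cost improvement, not a threat to the trial's main conclusions.

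**What to change.** In Protocol Section 6.3.2, add to both Baseline Visit lists an item collecting WI-NRS before the first application. Add a matching WI-NRS entry at Baseline in Table 4. Record the score in the eCRF beside I-NRS and name it as the WI-NRS Baseline.

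In the SAP, either add the two WI-NRS endpoints with that baseline, or record their removal in Section 8. Without one of these, the new value would be collected but not analysed.

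The cost is one extra question at one visit, an eCRF field, a short SAP change and a minor protocol amendment with the sponsor approval and IRB/EC review that Section 11.1.2 requires.

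A separate, optional matter is whether to limit the time-to-improvement endpoint to subjects with a baseline WI-NRS of at least 4, since a lower starting score cannot fall by 4 points. The fix above does not depend on it.
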